6.2. Preparation/Handling/Storage/Accountability

Preparation/Handling/Storage

Vials must be stored in a secured location under controlled temperature with no access for unauthorized personnel. The study refrigerator/freezer must be equipped with a continuous temperature monitor and alarm and should be equipped with back-up power systems. If the study vaccine components are exposed to temperatures outside the specified temperature range, all relevant data will be sent to the sponsor to determine if the affected study vaccine components can be used or will be replaced. The affected study vaccine components must be quarantined and not used until further instruction from the sponsor is received.

An unblinded study-site pharmacist, or other qualified individual, who will have no other study function following vaccination, will prepare the appropriate vials and syringes, labeled with the participant's identification number, and provide the syringes for the study vaccine in a blinded manner to the blinded study vaccine administrator who will perform the injection. An unblinded study-site pharmacist, or other qualified individual, may also perform the vaccination but will have no other study function following vaccination.

Refer to the Investigational Product Preparation Instructions and Study Site Investigational Product and Procedures Manual for additional guidance on study vaccine preparation, handling, and storage.

Accountability

The investigator is responsible for ensuring that all study vaccine received at the study site is inventoried and accounted for throughout the study. The study vaccine administered to the participant must be documented on the vaccine accountability form. All study vaccine will be stored and disposed of according to the sponsor's instructions.

Study vaccine must be handled in strict accordance with the protocol and the container label, and must be stored at the study site in a limited-access area or in a locked cabinet under appropriate

environmental conditions. Unused study vaccine must be available for verification by the sponsor's study-site monitor during on-site monitoring visits. The return to the sponsor of unused study vaccine will be documented on the vaccine return form. When the study site is an authorized destruction unit and study vaccine supplies are destroyed on site, this must also be documented on the vaccine return form.

Potentially hazardous materials containing hazardous liquids, such as used ampules, needles, syringes, and vials, should be disposed of immediately in a safe manner and therefore will not be retained for vaccine accountability purposes.

Study vaccine should be dispensed under the supervision of the investigator or a qualified member of the study-site personnel, or by a hospital/clinic pharmacist. Study vaccine will be supplied only to participants participating in the study. Study vaccine may not be relabeled or reassigned for use by other participants. The investigator agrees neither to dispense the study vaccine from, nor store it at, any study site other than the study sites agreed upon with the sponsor.

6.3. Measures to Minimize Bias: Randomization and Blinding

Study Vaccine Allocation

Procedures for Randomization

Central randomization will be implemented in this study. Within each cohort, participants will be randomly assigned to the groups based on a computer-generated randomization schedule prepared before the study by or under the supervision of the sponsor. In Cohort 1, the randomization ratio is 2:2:2:2:1 to Groups 1 to 5, respectively, in Cohort 2, the randomization ratio is 2:2:1 to Groups 6 to 8, respectively, and in Cohort 3, the randomization ratio is 1:2:1 to Groups 9 to 11, respectively. The randomization will be balanced by using randomly permuted blocks. The IWRS will assign a unique code, which will dictate the group assignment for the participant. The requestor must use his or her own user identification and personal identification number when contacting the IWRS, and will then give the relevant participant details to uniquely identify the participant.

If randomized participants discontinue from the study before the study vaccine is administered, additional participants may be recruited to replace these participants at the discretion of the sponsor. Any replacement participant will be assigned to the same group as the original (discontinued) participant. The replacement participant's randomization number will equal the randomization number of the discontinued participant +1000 (eg, participant 0001 would be replaced by participant 1001). These additional participants should also be randomized through IWRS. No replacements or additional randomizations will be done for withdrawals after vaccination.

Blinding

The investigator will not be provided with randomization codes until database lock of the final analysis of the complete study. The codes will be maintained within the IWRS, which has the functionality to allow the investigator to break the blind for an individual participant.

At the sponsor level, unblinding (at the participant level) will occur at the time of the primary analysis for each cohort (Section [9.5](#)). From the primary analysis onwards, group level results may be shared as needed, however, efforts will be made to preserve the blinding to the individual participant allocation.

Data that may potentially unblind the study vaccine assignment (eg, immunogenicity data, study vaccine preparation/accountability data, study vaccine allocation) will be handled with special care to ensure that the integrity of the blind is maintained and the potential for bias is minimized. This can include making special provisions, such as segregating the data in question from view by the investigators, clinical team, or others as appropriate until the time of database lock and unblinding.

The investigator may in an emergency determine the identity of the study vaccine by contacting the IWRS. While the responsibility to break the study vaccine allocation code in emergency situations resides solely with the investigator, it is recommended that the investigator contacts the sponsor if possible to discuss the particular situation, before breaking the blind. Telephone contact with the sponsor will be available 24 hours per day, 7 days per week. In the event the blind is broken, the sponsor must be informed as soon as possible. The date, time, and reason for the unblinding must be documented by the IWRS, in the appropriate section of the eCRF, and in the source document. The documentation received from the IWRS indicating the code break must be retained with the participant's source documents in a secure manner. The investigator is advised not to reveal the study vaccine assignment to the study-site personnel or sponsor personnel/sponsor representative.

The pharmacist or qualified individual with primary responsibility for study vaccine preparation and dispensing will be unblinded to study vaccine allocation (Section [6.2](#)).

Participants who have had their study vaccine assignment unblinded should continue to return for scheduled evaluations.

6.4. Study Vaccine Compliance

Study vaccine will be IM administered by a blinded study vaccine administrator (ie, a trained and qualified study nurse, medical doctor, or otherwise qualified healthcare professional) at the study site. The unblinded study-site pharmacist, or other qualified individual, may also perform the vaccination, but will have no other study function following vaccination. Details of each administration will be recorded in the eCRF (including date and time of injection). For blinding procedures, see Section [6.3](#).

6.5. Concomitant Therapy

Prestudy therapies administered up to 30 days before vaccination must be recorded in the eCRF at screening (all cohorts) and additionally on Day 1 for Cohorts 2 and 3.

Concomitant therapies such as analgesic/antipyretic medications and nonsteroidal anti-inflammatory drugs, corticosteroids, and antihistaminic must be recorded in the eCRF until 28 days after vaccination. All other concomitant therapies should also be recorded in the eCRF if administered in conjunction with new or worsening AEs reported per protocol requirements outlined in Section 10.3, Appendix 3.

Analgesic/antipyretic medications and nonsteroidal anti-inflammatory drugs may be used after vaccination only in cases of medical need (eg, fever or pain). Use of these medications as routine prophylaxis before vaccination is discouraged.

Information on concomitant use of herbal supplements or vitamins will not be collected.

Use of systemic corticosteroids must be documented during the study. Use of ocular, topical, or inhaled steroids during the study is allowed, whereas chronic (>10 days) or recurrent use of systemic corticosteroids during the study is prohibited. Antineoplastic and immunomodulating agents or radiotherapy are prohibited during the study. If chronic use of systemic corticosteroids or antineoplastic or immunomodulating agents becomes medically indicated during the study for any participant, the sponsor should be notified.

Vaccination with licensed live attenuated vaccines within 28 days of study vaccination (ie, before or after) is prohibited. Other licensed (not live) vaccines (eg, influenza, tetanus, hepatitis A, hepatitis B, rabies) should be given at least 14 days before (or at least 14 days after) administration of study vaccine in order to avoid potential confusion of adverse reactions and potential immune interference. If a vaccine is indicated in a postexposure setting (eg, rabies or tetanus), it must take priority over the study vaccine.

Use of any experimental medication (including experimental vaccines other than the study vaccine) during the study is not allowed.

The sponsor must be notified in advance (or as soon as possible thereafter) of any instances in which prohibited therapies are administered.

6.6. Intervention After the End of the Study

Participants will be instructed that study vaccine will not be made available to them after they have completed/discontinued study vaccination.

7. DISCONTINUATION OF STUDY VACCINATION AND PARTICIPANT DISCONTINUATION/WITHDRAWAL

7.1. Discontinuation of Study Vaccination

A participant's study vaccination must be discontinued if:

- The participant withdraws consent to receive study vaccination.
- The investigator believes that for safety reasons or reactogenicity reasons (eg, AE) it is in the best interest of the participant to discontinue study vaccination.

Study vaccine assigned to the participant who discontinued study vaccination may not be assigned to another participant. Additional participants will be entered to ensure the protocol-specified number of participants complete the study.

7.2. Contraindications to Study Vaccination

The following events assessed by the investigator constitute a temporary contraindication to study vaccination:

- Acute illness at the planned time of vaccination. This does not include minor illnesses, such as diarrhea or mild upper respiratory tract infection.
- Fever (body temperature of $\geq 38.0^{\circ}\text{C}$ [$\geq 100.4^{\circ}\text{F}$]) at the planned time of vaccination.

If any of these events occur at the planned time of vaccination, the participant may be vaccinated up to, and no later than, 10 days after the planned vaccination, or be withdrawn from vaccination at the discretion of the investigator.

Note: For participants in Cohorts 2 and 3, clinical safety laboratory assessments should be repeated if vaccination is postponed and the time between clinical safety laboratory assessments and vaccination exceeds 28 days.

7.3. Study Vaccination Pausing Rules

The PI(s) and sponsor team members (ie, SRP/SRS) will monitor the study vaccination pausing rules listed below. If vaccination is considered to raise significant safety concerns (ie, if at least one of the study vaccination pausing rules has been met), further vaccination of participants will be paused until the DRC review of all available data is carried out and subsequent communication between the sponsor and the PI(s) takes place. The DRC will review blinded data first but is entitled to and has the right to require submission of unblinded data if deemed necessary. When a first DRC meeting has been triggered by the occurrence of a given study vaccination pausing rule, the DRC will convene thereafter for each additional participant meeting that pausing rule. Possible actions upon review include, but are not limited to, study suspension, study adaptation, or discontinuation of further vaccination.

The following list of study vaccination pausing rules applies for concerned AEs that occur up to 28 days after vaccination and concerned SAEs:

1. One or more participants experience an SAE or other potentially life-threatening (Grade 4) event that is determined to be related to study vaccine; OR
2. One or more participants experience anaphylaxis clearly not attributable to other causes than vaccination with study vaccine; OR
3. Two or more participants experience a Grade 3 or 4 unsolicited AE of the same type, determined to be related to study vaccine, that persists for 72 hours or longer; OR
4. Two or more participants experience a Grade 3 or 4 solicited systemic AE of the same type, determined to be related to study vaccine, that persists for 72 hours or longer; OR
5. Two or more participants experience a persistent (upon repeated testing) Grade 3 or 4 laboratory abnormality related to the same laboratory parameter and considered related to study vaccine, that persists for 72 hours or longer; OR
6. Death of any participant considered related to study vaccine or if the causal relationship to study vaccine cannot be excluded.

Note: All cases of death will be sent to the DRC. Upon their review, the DRC will decide whether a study pause is required.

For study vaccination pausing rule 5: to assess abnormal laboratory values, the test must be repeated at least once, within 48 hours of the study site becoming aware of the abnormal value.

After each DRC review of similar AEs, the DRC will indicate the conditions under which it requires further notification and review of the subsequent similar AEs.

To enable prompt response to a situation that could trigger study vaccination pausing rules 3, 4, or 5, the investigator should update the eCRF with information on any Grade 3 or 4 AE on the same day that the AE is reported.

Also, the investigator should notify the sponsor's medical monitor (AND transmit the SAE form electronically to Global Medical Safety Operations, if applicable), immediately and no later than 24 hours after becoming aware of any related AE of Grade 3 or above AND update the eCRF with relevant information on the same day the AE information is collected. A thorough analysis of all Grade 3 (or above) cases will be carried out by the sponsor's medical monitor, irrespective of whether the criteria for pausing the study are met. Based on the pausing criteria, the sponsor's medical monitor will then decide whether a study pause is warranted. All study sites will be notified immediately in case of a study pause. The sponsor's medical monitor is responsible for the immediate notification of the DRC members and coordination of a DRC meeting in case of a study pause.

Vaccinations for the study may be suspended for safety concerns other than those described above, or before study vaccination pausing rules are met, if, in the judgment of the DRC, participant safety may be threatened.

Resumption of vaccinations will start only upon receipt by the study site of written recommendations by the DRC. The study site(s) will be allowed to resume activities upon receipt of a written notification from the sponsor. The communications from the DRC will be forwarded by the investigator to the Independent Ethics Committee (IEC)/Institutional Review Board (IRB) and by the sponsor to the relevant health authorities, according to local standards and regulations.

In addition to the study vaccination pausing rules, the sponsor's medical monitor or the PI(s) (upon consultation with the sponsor's medical monitor) may initiate a DRC review for any single event or combination of events which, in their professional opinion, could jeopardize the safety of the participants or the reliability of the data.

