 - After vaccination, participants will enter a 6-month safety and immunogenicity follow-up period. All AEs, serious adverse events (SAEs), and clinically significant laboratory abnormalities (including those persisting at the end of the study/early withdrawal) will be followed by the investigator until clinical resolution or until a clinically stable endpoint is reached, or until the participant has been deemed lost to follow-up after demonstration of due diligence of follow-up efforts. An early exit visit will be conducted for those participants who are unable to continue participation in the study and withdraw from the study before Day 183, but who do not withdraw consent. Participants who wish to withdraw consent from participation in the study will be offered an early exit visit (prior to formal withdrawal of consent) (Section 7.4).

- Several safety measures are included in this protocol to minimize the potential risk to participants, including the following:
 - An internal Data Review Committee (DRC) will be commissioned for this study (Section 9.6). In addition to the planned review of postvaccination safety data of participants in Cohorts 2 and 3, the DRC will be consulted if at least one of the study vaccination pausing rules has been met and/or if the participant's safety may be threatened.
 - There are prespecified rules that would result in pausing of further vaccination of participants if predefined conditions occur, preventing exposure of new participants to study vaccine until the DRC reviews all available safety data and subsequent communication between the sponsor and the PI(s) takes place (Section 7.3). When a first DRC meeting has been triggered by the occurrence of a given study vaccination pausing rule, the DRC will convene thereafter for each additional participant meeting that pausing rule. Possible actions upon review include, but are not limited to, study suspension, study adaptation, or discontinuation of further vaccination.
 - In Cohort 2, a sentinel group of 5 participants will be enrolled before enrolling additional participants (Step 1) (Section 4.1). In the absence of any clinical safety concerns upon a blinded 24-hour postvaccination safety review, an additional 15 participants will be enrolled (Step 2). After review of the 7-day (Day 8) postvaccination safety data of these 20 participants by the DRC, the remaining participants will be enrolled (Step 3).

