An AE is considered unlisted if the nature or severity is not consistent with the applicable product reference safety information. For the Ad26/protein preF RSV vaccine, the expectedness of an AE will be determined by whether or not it is listed in the respective IB.

ATTRIBUTION DEFINITIONS

Causality of AEs should be assessed by the investigator based on the following:

Related: there is a reasonable possibility that the study vaccine contributed to the AE.

Unrelated: there is no suspicion that there is a relationship between the study vaccine and the AE; there are other more likely causes and administration of the study vaccine is not suspected to have contributed to the AE.

By definition, all solicited AEs at the injection site will be considered related to the study vaccine administration.

SEVERITY CRITERIA

All AEs and laboratory data will be coded for severity using a modified version of the FDA grading table, based on version of September 2007¹⁶, included in Section 10.2, Appendix 2.

For AEs not identified in the grading table, the following guidelines will be applied:

Grade 1	Mild	Symptoms causing no or minimal interference with usual social and functional activities
Grade 2	Moderate	Symptoms causing greater than minimal interference with usual social and functional activities
Grade 3	Severe	Symptoms causing inability to perform usual social and functional activities and requires medical intervention
Grade 4	Potentially life-threatening	Symptoms causing inability to perform basic self-care functions OR medical or operative intervention indicated to prevent permanent impairment, persistent disability OR ER visit or hospitalization

SPECIAL REPORTING SITUATIONS

Safety events of interest on a sponsor study vaccine in an interventional study that may require expedited reporting or safety evaluation include, but are not limited to:

- Overdose of a sponsor study vaccine
- Suspected abuse/misuse of a sponsor study vaccine
- Accidental or occupational exposure to a sponsor study vaccine

- Medication error, intercepted medication error, or potential medication error involving a Johnson & Johnson medicinal product (with or without patient exposure to the Johnson & Johnson medicinal product, eg, product name confusion, product label confusion, intercepted prescribing or dispensing errors)

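### The note under pausing rule 6 has the DRC review any death before a pause is decided, whereas Sections 7.3 and 2.3.5 put the pause first once a rule is met

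*Protocol*

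**What the plan says.** The lead-in to Protocol Section 7.3 makes the pause automatic. If at least one rule is met, "further vaccination of participants will be paused until the DRC review of all available data is carried out" and the sponsor and principal investigators have then communicated. Section 2.3.5 relies on this in the benefit-risk argument and describes the rules as "preventing exposure of new participants to study vaccine until the DRC reviews all available safety data".

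Rule 6 is triggered by "Death of any participant considered related to study vaccine or if the causal relationship to study vaccine cannot be excluded". Directly beneath it stands the note: "Note: All cases of death will be sent to the DRC. Upon their review, the DRC will decide whether a study pause is required".

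Three other provisions bear on the point:

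- Rule 1 is met when "One or more participants experience an SAE or other potentially life-threatening (Grade 4) event that is determined to be related to study vaccine".
- Under Attribution Definitions in Appendix 3 (Section 10.3), causality is either related or unrelated, and an event is unrelated when "there is no suspicion that there is a relationship between the study vaccine and the AE" and other causes are more likely.
- Appendix 3 also makes every death in the study a reportable SAE, and Section 8.3.1 requires SAEs to reach the sponsor within 24 hours of the site learning of them.

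**The concern.** A pausing rule should give one instruction. For a death that meets rule 6, the lead-in stops vaccination first and the DRC reviews afterwards. The note sends the death to the DRC first and makes the pause an outcome of that review. Both the order and the decision-maker differ.

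A sponsor or site that followed the note literally could go on vaccinating until the DRC had met, which is the exposure Section 2.3.5 says the rules prevent. The protocol sets no time limit for the DRC's review of a death. The setting gives the point some weight: participants are aged 60 or older, the study is multicenter, Cohorts 1 and 2 may enrol in parallel, and Cohorts 2 and 3 use Ad26.RSV.preF doses above any with existing safety data (Sections 4.1 to 4.3).

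**Working it through.** No arithmetic beyond a count applies. The check compares the instructions and then asks which deaths depend on rule 6 alone.

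**Step 1. The order of events in each place.**

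| Place | Order |
|---|---|
| 7.3, lead-in | Rule met → pause → DRC review → sponsor and PI communication |
| 2.3.5 | Rule met → pause → DRC review |
| 7.3, text after the rules | Medical monitor decides on a pause from the criteria → DRC notified and meeting arranged |
| 7.3, note to rule 6 | Any death → DRC review → DRC decides whether to pause |

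Three of the four agree, and the note is the exception. Section 9.6 and SAP Section 3 say that the DRC discusses situations meeting a pausing rule, but they do not settle the order.

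**Step 2. Which rules can a death meet if it is not classed as related but causality cannot be excluded?**

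| Rule | Causality condition | Met by such a death? |
|---|---|---|
| 1 | SAE or Grade 4 event determined to be related | No |
| 2 | "One or more participants experience anaphylaxis clearly not attributable to other causes than vaccination with study vaccine" | Only if anaphylaxis |
| 3 | Unsolicited Grade 3 or 4 events determined to be related | No |
| 4 | Solicited systemic Grade 3 or 4 events determined to be related | No |
| 5 | Laboratory abnormality: "related to the same laboratory parameter and considered related to study vaccine" | No |
| 6, first limb | Considered related | No |
| 6, second limb | Relationship cannot be excluded | Yes |

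Four of the 6 rules (1, 3, 4 and 5) need a judgement of relatedness, and rule 2 needs anaphylaxis. For a death that is not anaphylaxis, that leaves 6 − 4 − 1 = 1 rule, met through its second limb.

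**Step 3. The effect of the note by type of death.**

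- *Classed as related.* The death meets rules 1 and 6. The note conflicts with the lead-in, but rule 1 carries no such note and pauses vaccination anyway.
- *Not classed as related, causality not excluded, not anaphylaxis.* Only the second limb of rule 6 applies. Here the conflict has a practical effect.
- *Meets no pausing rule.* No automatic pause exists. The note adds a referral to the DRC and causes no conflict.

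**Step 4. How large is the middle group?** It is small. Because unrelated requires the absence of any suspicion, most deaths whose causality cannot be excluded should be classed as related and so fall in the first group. The middle group is mainly deaths for which the causality assessment is not yet complete.

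**The case against.** The best answer is that the texts can be read together. The lead-in covers every rule, rule 6 included, and the note neither suspends it nor says that vaccination continues meanwhile. The note's subject is wider than rule 6, so its natural purpose is to refer deaths that rule 6 does not reach. It could also mean that the DRC decides whether a pause already in force should continue. The conflicting reading would leave rule 6 with little purpose as a pausing rule.

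Other text in Section 7.3 also helps. The medical monitor analyses all cases of Grade 3 or above whether or not a rule is met and then applies the pausing criteria. The monitor or a principal investigator may start a DRC review for any single event, and the DRC may suspend vaccination before a rule is met. Each participant receives one injection, so a pause protects only people not yet dosed and has no effect once enrolment closes.

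Much of this stands. The first reading is probably what was intended, and the other powers narrow the gap. They do not close it. The note covers all deaths without exception, and its position under rule 6 invites its use for deaths that meet the rule. Asking whether a pause is required suggests that none is yet in force; Section 7.3 speaks of resumption when it means lifting one. The discretionary powers allow a pause but do not require one. The DRC charter may set a review time, but it is not among the documents and would not change the protocol's wording.

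**Conclusion.** The concern holds: for a death meeting rule 6, the note as written conflicts with the pause-first order in Sections 7.3 and 2.3.5. Its weight is low, and the change is one the sponsor could make rather than must make. It affects no endpoint, analysis set, estimate or sample size.

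The consequence is confined to a death that is not anaphylaxis and not classed as related, whose causality cannot be excluded, and that occurs while participants are still being vaccinated. For it, the 1 rule of 6 that applies is the one the note obscures. The count describes coverage of the rules and does not measure risk. The documents give neither an enrolment rate nor a DRC convening time, so no number of exposed participants is claimed. The conclusion rests on the protocol text alone, without the DRC charter.

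**What to change.** Replace the note under rule 6 in Section 7.3 with wording such as:

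> Every death is referred to the DRC. A death that meets rule 6, or any other pausing rule, pauses vaccination immediately, pending DRC review. For any other death, the DRC decides on review whether a pause is needed.

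This keeps the referral of all deaths and the DRC's discretion where no rule is met. It adds no data, visits or procedures. The cost is an occasional short pause for a death later judged unrelated, which rule 6 and the lead-in already imply. An immediate pause is workable because every death is already reportable to the sponsor within 24 hours.
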